4.3.8. Blinding and Unblinding

This is a randomized, double-blind study.

The subject, investigator, study coordinator, sponsor, and the entire study processing team will remain blinded to treatment assignment. The blind can be broken only if the investigator deems it necessary for the safe treatment of a subject, and whenever possible the medical monitor and sponsor should be consulted before breaking the blind.

If the blind is broken for any reason during the course of the study, the moment on which the subject's data were unblinded and all other relevant information will be documented by the investigative site, the CRO, and other sponsor designees, as appropriate. The reason for breaking the blind will be indicated and justified in the source documentation and in the eCRF. The blind can be broken by the investigator via the [REDACTED] system.

All subjects who are unblinded while on the study will be withdrawn at the moment of unblinding, with the reason for unblinding given as the reason for discontinuation from the study. If an AE leads to unblinding, the AE should be given as the reason for unblinding and the AE should also be recorded in the eCRF. All subjects who are unblinded should, where possible, complete the EDV. AEs will be recorded from the signature of the ICF until the final follow-up visit. In case an AE is ongoing at that time, it will be followed up until resolution or until stabilization by the investigator as much as possible.

5. STUDY ASSESSMENTS

5.1. TIMING OF ASSESSMENTS

The study assessments as described below will be performed at the time points specified in the study flow chart, provided in Section 1. Visits are to be scheduled within a window of ± 2 (Visits 3 and 4) or 3 days (Visits 5, 6, 7, and the follow-up visit) and in such a way that the total study duration from baseline to last dosing does not exceed 13 weeks.

The sequence of study assessments, if planned at one study visit, will be as follows (if applicable):

1. physical examination, oral body temperature, ECG, systolic and diastolic blood pressure (SBP and DBP), supine heart rate, respiratory rate
2. SGRQ
3. assessment of (S)AE(s) and concomitant medication
4. blood sampling for PK
5. blood sampling for safety laboratory analysis
6. blood sampling for PD
7. blood sampling for biomarkers

8. spirometry ¹⁶
9. DLCO ¹⁶
10. HRCT-scan ¹⁶
11. bronchoscopy (biomarkers and PD in BALF)

5.2. INITIAL SUBJECT AND DISEASE CHARACTERISTICS

Written informed consent must be obtained before any study-related procedures take place. During the screening period, following signing of the ICF, the subject's historical HRCT and SLB (if available) will be sent to the central reader for the confirmation of the IPF diagnosis through a:

- central review of chest HRCT
- central review of SLB (if available)

Note that both the chest HRCT and SLB need to be sent to central review at least 8 days prior to the baseline visit to allow for central reading and confirmation of IPF diagnosis. Additional details are provided in Appendix 2.

In addition, information on demographics and medical history/concomitant diseases (including the multidisciplinary diagnosis of IPF at the site, the duration of disease, disease progression prior to screening, the medications used to treat the disease, drinking, and smoking habits) will be collected. A physical examination will take place and vital signs, ECG, clinical laboratory assessments (including serology, FSH [if applicable]), spirometry, and DLCO will be conducted to determine the subject's eligibility for study participation.

Note that if screening spirometry measurements fail to meet acceptability and repeatability criteria as specified by the American Thoracic Society (ATS)/European Respiratory Society (ERS) guidelines (Miller, Hankinson, & Brusasco, 2005), repeat spirometry evaluation may be performed once. If repeat values are within the acceptability criteria and completed within the screening window, the subject is eligible for the study.

At baseline, after the subject's eligibility for the study has been confirmed, the subject will be randomized into the study to receive treatment with GLPG1690 600 mg *q.d.* or placebo. Study drug will be dispensed and all subjects will be handed a diary card (additional information is provided in Section 5.3). All baseline assessments are specified in the study flow chart, provided in Section 1.

5.3. SUBJECT DIARY CARD

Subjects will be given a diary card at Day -1 (baseline) to record the following:

- From Day 1 through Day 84 (or the EDV), subjects will be asked to record the date (and time) of study drug intake and the number of capsules taken for each administration.
- From Day 1 to Day 84 (or the EDV), subjects will be asked to indicate whether a home-based spirometry test was done and if no such test was done, the reason(s) why should be provided.

¹⁶ Subjects taking inhaled bronchodilators can do this after spirometry assessments (and DLCO) and prior to the performance of the HRCT.

- From Day 1 to Day 84 (or the EDV), subjects will be asked to record changes in concomitant medication regimen, including new medicines not captured in medication history, use of bronchodilators, any other concomitant medication used as well as any emerging AE.

Subjects will be instructed to bring the diary card and used/unused study drug to each visit. All diary card data will be entered in the eCRF by the designated site personnel.

5.4. SAFETY ASSESSMENTS

The safety and tolerability assessment will be based on the collection of AEs (including IPF exacerbations), physical examinations, vital signs measurements, 12-lead ECG, and safety laboratory assessments (standard hematology, serum/plasma chemistry, coagulation tests, and urinalysis).

5.4.1. Adverse Events

AEs will be reported and documented as described in Section 8.

5.4.1.1. Acute IPF Exacerbation

All acute IPF exacerbations will be reported and documented as (S)AEs (see Section 8). An acute IPF exacerbation is defined as an acute and clinically significant deterioration of unidentifiable cause in patients with underlying IPF. Diagnostic criteria are defined as follows (Collard, et al., 2007):

1. The subject has a previous or concurrent diagnosis of IPF.
2. The subject shows unexplained worsening or development of dyspnea within 30 days.
3. The HRCT shows new bilateral ground-glass abnormality and/or consolidation superimposed on a background reticular or honeycomb pattern consistent with usual interstitial pneumonia pattern.
4. There is no evidence of pulmonary infection by endotracheal aspirate or bronchoalveolar lavage ¹⁷.
5. Alternative causes, including the following, are excluded:
 - left heart failure
 - pulmonary embolism
 - identifiable cause of acute lung injury ¹⁸

¹⁷ Evaluation of samples should include studies for routine bacterial organisms, opportunistic pathogens and common viral pathogens.

¹⁸ Causes of acute lung injury include sepsis, aspiration, trauma, reperfusion pulmonary edema, pulmonary contusion, fat embolization, inhalational injury, cardiopulmonary bypass, drug toxicity, acute pancreatitis, transfusion of blood products, and stem cell transplantation.

5.4.2. Clinical Laboratory Evaluations

Blood samples of approximately 16 mL (or approximately 21 mL at screening only) will be collected predose by venipuncture (or indwelling catheter for pharmacokinetic sampling days) in the arm at the time points indicated in the study flow chart (provided in Section 1) and according to sequence of study assessments as described in Section 5.1. In addition, urine samples for the clinical laboratory assessments will be collected. Subjects do not need to be fasted at the time of sampling.

Blood and urine samples will be collected for the following clinical laboratory tests:

- hematology: hematocrit, hemoglobin, red blood cell count, WBC total count, WBC differential count (absolute and relative), and platelets
- serum/plasma chemistry: glucose, urea, creatinine, uric acid, sodium, potassium, calcium, chloride, phosphorus, AST, ALT, gamma glutamyl transferase, total bilirubin, alkaline phosphatase, albumin, total proteins, triglycerides, cholesterol, and brain natriuretic peptide
- coagulation parameters: international normalized ratio and partial thromboplastin time
- urinalysis: pH, glucose, proteins (quantitative); ketones, and microscopic examination of the sediment (cylinders, erythrocytes, leucocytes)
- serology: hepatitis B surface antigen, hepatitis B virus antibody, HIV-1 and HIV-2 antibody (only at screening)
- FSH (only at screening in case there is doubt on whether a female subject is postmenopausal)

The laboratory values outside the normal range will be flagged and clinical relevance will be assessed by the investigator. More frequent sampling as well as additional tests may be performed as deemed necessary by the investigator to follow-up and resolve any safety concerns.

Note that in case clinically significant laboratory test results are a potential reason for discontinuation from the study drug and withdrawal from the study, retesting should be prompt (within 3 to 5 days) after the investigator has consulted with the medical monitor. A decision regarding subject discontinuation should be made only after the results from the retest are available (see Section 4.2.5 for additional information).

The details of sample handling and shipment instructions will be provided in a separate laboratory manual.

5.4.3. Vital Signs

Vital signs will be measured predose at the time points indicated in the study flow chart (provided in Section 1) and according to sequence of study assessments as described in Section 5.1. Vital signs must be taken after 5 min in the supine position, prior to the bronchoscopy.

Vital signs will include supine heart rate, respiratory rate, SBP, DBP, and oral body temperature.

Normal ranges are provided in Appendix 4.

5.4.4. Physical Examination

The physician (or a trained assistant or nurse practitioner, as applicable by local regulations) will perform a full physical examination (including ear, nose, throat, neck, chest, abdomen, and extremities) predose at the time points indicated in the study flow chart (provided in Section 1) and according to sequence of study assessments as described in Section 5.1.

Height and weight will be measured at screening only (with shoes off).

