1. STUDY FLOW CHART

EVENT	Visit 1 Screening	Visit 2 Baseline	DOSING PERIOD						EDV	FU
				Visit 3 ¹ W1	Visit 4 ¹ W2	Visit 5 ¹ W4	Visit 6 ¹ W8	Visit 7 ¹ W12		
Visit										Visit 8/ EOS W14
Study days (D)	D-28 to D-4	D-1	D1	D7 ±2 days	D14 ±2 days	D28 ±3 days	D56 ±3 days	D84 ±3 days		D98 ±3 days
Informed consent	X									
Historical HRCT sent to central review ²	X									
SLB sent to central review ^{2,3}	X									
Demographics	X									
Medical history/Concurrent illnesses	X									
Inclusion/exclusion criteria	X									
Serology	X									
FSH test ⁴	X									
DLCO	X									
Confirm all eligibility criteria		X								
Randomization		X								

¹ Subjects will be asked to come to the study center in the morning at approximately the same time on every visit.

² The HRCT and SLB need to be sent to central review at least 8 days prior to the baseline visit to allow for central reading and confirmation of diagnosis.

³ If available

⁴ Only at screening in case there is doubt on whether a female subject is postmenopausal.

EVENT	Visit 1 Screening	Visit 2 Baseline	DOSING PERIOD						EDV	FU
				Visit 3 ¹ W1	Visit 4 ¹ W2	Visit 5 ¹ W4	Visit 6 ¹ W8	Visit 7 ¹ W12		
Visit										
Study days (D)	D-28 to D-4	D-1	D1	D7 ±2 days	D14 ±2 days	D28 ±3 days	D56 ±3 days	D84 ±3 days		D98 ±3 days
Dispense study drug		X		X	X	X	X			
Collect study drug				X	X	X	X	X	X	
Study drug intake ⁵				On a daily basis						
Check study drug accountability and compliance				X	X	X	X	X	X	
Diary card dispensing		X		X	X	X	X			
Diary card collection				X	X	X	X	X	X	
Clinical laboratory tests ⁶	X	X		X	X	X	X	X	X	X
Vital signs ⁷	X	X		X	X	X	X	X	X	X
Physical examination ⁸	X	X		X	X	X	X	X	X	X
12-Lead ECG ⁹	X			X	X	X	X	X	X	X
PK blood samples ¹⁰		X		X	X	X	X	X	X	X

⁵ Subjects will begin to take treatment the morning following randomization (*i.e.*, on Day 1). Study drug intake at Visits 3, 4, 5, 6, and 7 will take place at the study center after all predose assessments have been performed.

⁶ Clinical laboratory tests include hematology, serum/plasma chemistry, coagulation, and urinalysis.

⁷ Vital signs include blood pressure, respiratory rate, heart rate, and oral temperature.

⁸ Height and weight will be measured at screening only.

⁹ A 12-lead ECG will be performed after the subject has been in supine position for at least 5 minutes.

¹⁰ All PK samples will be taken predose. At Day 28, in addition to predose, samples will be taken 1.5 h, 4 h, and 6 h post dose

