2.3.4. Toxicology

2.3.4.1. General Toxicology

The dose-limiting effects in the repeated dose toxicity studies with GLPG1690 in the rat consisted of reduced food consumption (FC) and markedly decreased body weight (BW) gain at 1000 mg/kg/day for 4 weeks. In dogs, the dose-limiting effects corresponded to decreased white blood cells (WBCs) and FC, emesis and BW loss, associated with poor clinical conditions as reported at the dose of 150 mg/kg/day in the 13-week study.

In the 13-week study in rats, the no observed adverse effects level (NOAEL) was at the dose of 40 mg/kg/day in males and 400 mg/kg/day in females, corresponding to area under the concentration-time curve from time 0 to 24 hours (AUC_{0-24h}) values of 68.3 $\mu\text{g.h/mL}$ and 1680 $\mu\text{g.h/mL}$, respectively (which is approximately 0.9- and 22-fold higher, respectively, than the anticipated free plasma AUC_{0-24h} [0.532 $\mu\text{g.h/mL}$] in human after a 600 mg dose). In the 13-week study in dogs, the NOAEL was considered to be the dose of 50 mg/kg/day, corresponding to a mean AUC_{0-24h} of 1010 $\mu\text{g.h/mL}$ (which is approximately 21-fold higher than the anticipated free plasma AUC_{0-24h} [0.532 $\mu\text{g.h/mL}$] in human after a 600 mg dose). The clinical signs, the changes in hematological and clinical biochemistry, and the pathological findings observed at the NOAEL in the rat and dog were considered non-adverse because they were mild in intensity, had no functional or morphological adverse correlate, and were fully reversible after a 4-week treatment-free recovery period.

Reproductive embryo-fetal development studies were performed in rats and rabbits with GLPG1690. In rats, the maternal and developmental NOAELs for GLPG1690 were determined at 60 mg/kg/day and 10 mg/kg/day, respectively. These NOAELs correspond to a mean AUC_{0-24h} of 324 and 21.4 $\mu\text{g.h/mL}$ on Day 17 post-coitum, respectively, which is

approximately 4- and 0.3-fold higher than the anticipated free plasma AUC_{0-24h} (0.532 $\mu\text{g.h/mL}$) in human after a 600 mg dose. In rabbits, the maternal and developmental NOAELs were concluded to be 15 mg/kg/day and 5 mg/kg/day, respectively. These NOAELs correspond to a mean AUC_{0-24h} of 50.8 $\mu\text{g.h/mL}$ and 8.10 $\mu\text{g.h/mL}$ on Day 16 post-coitum, respectively (which is approximately 0.4- and 0.06-fold higher than the anticipated free plasma in human after a 600 mg dose).

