3. STUDY OBJECTIVES

3.1. PRIMARY OBJECTIVES

- to evaluate the safety and tolerability of GLPG1690
- to characterize the PK and PD properties of GLPG1690

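### Weight is taken at screening only, so a body-weight effect listed as dose-limiting in both animal species cannot be measured or compared between arms

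*Protocol*

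**What the plan says.** Two places in the protocol fix the weighing schedule, and they agree. Section 5.4.4 (Physical Examination) reads "Height and weight will be measured at screening only (with shoes off" and footnote 8 of the flow chart in Section 1 reads "Height and weight will be measured at screening only". Section 5.4.3 does not add weight by another route: "Vital signs will include supine heart rate, respiratory rate, SBP, DBP, and oral body temperature". No other section schedules a later weight.

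The first primary objective in Section 3.1 is "to evaluate the safety and tolerability of GLPG1690".

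Section 2.3.4.1 describes the dose-limiting effects in the two toxicology species. In the rat they "consisted of reduced food consumption (FC) and markedly decreased body weight (BW) gain at 1000 mg/kg/day for 4 weeks". In the dog, "the dose-limiting effects corresponded to decreased white blood cells (WBCs) and FC, emesis and BW loss, associated with poor clinical conditions", reported at 150 mg/kg/day in the 13-week study.

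Section 6.3.3 plans changes from baseline for the safety data but restricts physical examination results to listings.

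**The concern.** The protocol names a body-weight effect as dose-limiting in both species and then fixes a schedule that yields no weight after screening. This is a stated rule. A statistical analysis plan cannot repair it, because the data will not be collected.

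The other findings in the dog sentence are treated differently. White cells are followed by haematology at every visit from screening to follow-up. Weight is not followed at all, and the protocol gives no reason for the difference.

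Three features of the trial make the gap worth closing:

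- Section 2.4 gives the longest previous human dosing as 14 days, in healthy men. This trial doses patients with a debilitating disease for 12 weeks.
- The dog weight loss arose in a 13-week study, about the duration used here. Section 2.6 justifies 12 weeks of treatment by the 13-week limit of the preclinical safety data.
- The protocol reports no human weight-change data.

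At stake is whether the study report can say anything quantitative about weight under GLPG1690.

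**Working it through.** The protocol gives no figure to reproduce. Section 6.1 says that strict statistical criteria were not used to set the sample size. The check is therefore a count of visits, a comparison of the toxicology margins, and an illustration of what serial weights would deliver.

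**1. Visits without a weight (flow chart, Section 1)**

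| Visit | Physical examination | Haematology | Weight |
|---|---|---|---|
| Screening | yes | yes | yes |
| Day -1 (baseline) | yes | yes | no |
| Day 7, 14, 28, 56, 84 | yes | yes | no |
| Day 98 (follow-up) | yes | yes | no |
| Early discontinuation | yes | yes | no |

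Dosing starts on Day 1, so Day -1 is a pre-dose visit. The scheduled post-dose visits are Day 7, 14, 28, 56, 84 and 98, which is six, plus the early discontinuation visit. Weights at these visits: none. The single weight falls between Day -28 and Day -4, so it need not be close to the first dose.

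**2. Length of exposure**

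Twelve weeks is 84 days, against 14 days before: 84 / 14 = 6 times longer. This bears on how much human safety data exist. It is not evidence about weight.

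**3. Prior risk (Section 2.3.4.1)**

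- Dog: the no-effect dose is 50 mg/kg/day, at about 21-fold the anticipated free human exposure. Weight loss was reported at 150 mg/kg/day, and 150 / 50 = 3 times the no-effect dose.
- Rat, 13-week study: the no-effect margins are about 22-fold in females and 0.9-fold in males. The text does not say which finding set the male level. The reduced weight gain is reported at 1000 mg/kg/day.
- Coherence of the margins: implied free fraction = fold × 0.532 / AUC. Dog: 21 × 0.532 / 1010 = 1.1%. Female rat: 22 × 0.532 / 1680 = 0.70%. Male rat: 0.9 × 0.532 / 68.3 = 0.70%. These fall within the 0.4% to 2.1% implied by the 97.9% to 99.6% animal protein binding in Section 2.3.3, so the margins can be taken as stated.
- The protocol gives no exposure at the dose-limiting doses themselves.

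**4. What serial weights would deliver**

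About 24 subjects at 3:1 (Section 4.3.3) gives 18 active and 6 placebo. The SD of 12-week weight change is not in the document; 2, 3 and 4 kg are assumptions.

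- Within the active arm, 95% half-width = t(0.975; 17) × SD / √18 = 2.110 × SD / 4.243.
- Between arms, 95% half-width = t(0.975; 22) × SD × √(1/18 + 1/6) = 2.074 × SD × 0.471.
- Power for an assumed 3 kg difference, two-sided 5%, normal approximation = Φ(3 / (SD × 0.471) − 1.96).

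| Assumed SD | Within active arm | Between arms | Power for 3 kg |
|---|---|---|---|
| 2 kg | ±1.0 kg | ±2.0 kg | 89% |
| 3 kg | ±1.5 kg | ±2.9 kg | 56% |
| 4 kg | ±2.0 kg | ±3.9 kg | 36% |

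Under the current schedule none of these quantities can be estimated.

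**The case against.** The strongest reply is that the protocol is consistent with itself and that safety monitoring does not depend on weight. Much of this stands.

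- **Other routes exist.** Section 8.6 obliges the investigator to collect adverse events by observation and open questioning as well as spontaneous report. Diary cards record emerging events from Day 1 to Day 84. A full physical examination takes place at each visit, albumin, total protein and urinary ketones are measured repeatedly, and an independent pulmonologist reviews unblinded safety data. Emesis, which accompanied the dog weight loss, is open to adverse event reporting. A reader might infer that weight loss would go undetected. The document does not support that: marked loss could well be noticed. What these routes do not supply is a scheduled, quantitative change from baseline or a comparison between arms.
- **The animal signal is limited.** A reader might infer that weight loss was dose-limiting in both species. The rat finding was reduced gain; loss is stated only for the dog, as one of several effects. Both arose at high doses, and Section 2.5 places the main risk in fertility, pregnancy and lactation. Section 2.5 also names diarrhoea among the most common phase I events, but describes the events as at most moderate and transient, and nothing links them to weight. The animal data do not predict weight loss in this trial.
- **The trial is small.** Between arms, only a fairly large difference would be resolved. This is correct, and it limits what the fix can claim. It does not apply to within-arm estimates or to individual trajectories, which suit the descriptive analysis planned in Section 6.3.3.

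**Conclusion.** The point holds as a gap in measurement. The protocol schedules no weight at Day -1, at six post-dose visits or at early discontinuation, so change in weight cannot be estimated or compared, although the toxicology section lists body-weight effects among the dose-limiting findings in rat and dog and safety is a primary objective.

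It is not an internal contradiction: the two statements of the rule agree, and nothing in the protocol is false on this point. Prior risk is modest, given the 21-fold dog margin. The precision figures rest on 18 versus 6 subjects with complete weights and on an assumed SD of 2 to 4 kg. The visit count rests on the flow chart alone. The change is a cheap improvement that should be made.

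**What to change.** Amend footnote 8 of the flow chart and Section 5.4.4 so that height stays at screening only, while weight (shoes off) is taken at screening, at baseline (Day -1) and at the scheduled post-dose visits. The minimum useful set is Day -1, Day 84 or the early discontinuation visit, and follow-up. In Section 6.3.3, name weight explicitly and add a descriptive summary of its change from Day -1 by arm. Without that addition, weight would fall under the physical examination, which is only listed, since Section 5.4.3 does not count it as a vital sign.

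The cost is one scale reading at visits that already include a physical examination, one eCRF field and one table. No visit or invasive procedure is added. The report should present the between-arm comparison as descriptive and should not read a wide interval as evidence of no effect.

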5.4.5. Electrocardiogram

A 12-lead ECG will be performed predose at the time points indicated in the study flow chart (provided in Section 1) and according to sequence of study assessments as described in Section 5.1. The ECG must be taken after 5 min in the supine position, prior to any blood sampling. Each ECG will be interpreted by the investigator for clinical significance.

Normal ranges are provided in Appendix 4.

